8.3 Sample Size Determination

If sample size in each group is 20, (a total sample size of 40), we will have 89% power to detect a difference in means of 23 (the difference between A-tDCS mean change in accuracy, μ_1 , of 33 and a sham mean change in accuracy, μ_2 , of 10) assuming that the standard deviation of change for both groups is 22.2 using a two group *t*-test with a two-sided alpha of 0.05. These mean changes for tDCS and sham and standard deviation of change are based on the one published sham-controlled study of tDCS combined with SALT in subacute stroke (You et al, 2011).

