In this project, we will investigate the effects of transcranial direct current (tDCS) stimulation during language therapy for naming in individuals with aphasia in the acute and subacute post stroke period (i.e., within three months post stroke). Naming difficulties are a persistent and common symptom in aphasia after left-hemisphere (LH) stroke. Behavioral therapy (speech and language therapy; SALT) is the mainstay treatment for post stroke aphasia (Brady et al., 2012; Kurland et al., 2012). Therapy is beneficial for language recovery in stroke, especially in the first three months post stroke (Hillis, 2010; Lazar et al., 2010). Transcranial direct cortical stimulation (tDCS) is a promising adjunct to traditional SALT (Baker et al., 2010; Boggio et al., 2009; Ferrucci et al., 2008; Flöel et al., 2008; [name] et al., 2011; Monti et al., 2008; 2013; Schlaug et al., 2008). tDCS is a safe, non-invasive, non-painful electrical stimulation of the brain which modulates cortical excitability by application of weak electrical currents in the form of direct current brain polarization (Weiss & Bikson, 2014). It is usually administered via saline-soaked surface sponge electrodes attached to the scalp and connected to a direct current stimulator with low intensities (Lang et al., 2005). Research paradigms employing tDCS are based on principles of neuroplasticity. Anodal tDCS (A-tDCS) is most often applied to left hemisphere language areas to increase cortical excitability (reduce the threshold of activation). Most of studies are conducted in the chronic phase after stroke. Because neuroplasticity is greatest early after stroke, there is reason to believe tDCS might be most effective in the acute-subacute period. However, only two studies have evaluated tDCS paired with language therapy in group studies of acute to subacute aphasic stroke patients (Jung et al., 2011; You et al., 2011) and only one of these (You et al., 2011) was sham-controlled. Furthermore, no studies (of which we are aware) have combined A-tDCS with therapy to facilitate *naming* in post stroke aphasia, as shown to be effective in studies of chronic stroke (Baker et al., 2010).

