Most of studies are conducted in the chronic phase after stroke. Only two studies have evaluated tDCS paired language therapy in group studies of acute to sub-acute aphasic stroke patients (Jung et al., 2011; You et al., 2011) and only one of these (You et al., 2011) was sham-controlled. In the Jung et al. (2011) study, the individuals with milder degrees of aphasia made the greatest language improvements following ten days of therapy paired with tDCS. You and colleagues (You et al., 2011) evaluated 2mA tDCS over superior temporal gyrus (STG) paired with language therapy in 21 aphasic individuals, comparing three groups of seven patients each who received: cathodal right STG, anodal left STG, or sham tDCS. Greater gains in auditory comprehension were observed in patients who received cathodal tDCS (17%) compared to sham (10%) or anodal tDCS (10%). However, those who received cathodal tDCS were the least impaired on auditory comprehension at baseline, making it difficult to sort out the effects of tDCS. Furthermore, four of seven patients in the anodal tDCS group had lesions of the left STG, so it is not clear that they had structurally intact cortex beneath the left STG stimulating electrode, which may account for the negative results compared to sham. Thus, there is insufficient evidence to determine if tDCS augments SALT in facilitating aphasia recovery at the acute or sub-acute stage post stroke. However, these two studies show that in a fairly large number of patients (n=58) that 1-2mA tDCS is well tolerated and safe when delivered for 10 days in combination with language therapy.

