The primary analysis will compare change in accuracy of naming untrained items between groups (A-tDCS versus sham) in a two-sample *t*-test for the Intent-to-treat sample. For participants who do not complete the Week 1 post-treatment assessment, the post-treatment value will be imputed using a multiple imputation approach assuming a monotone missing mechanism and missing is at random (MAR). As a sensitivity analysis, the primary outcome analysis will be repeated using all available follow-up data (without explicit imputation) in a mixed effects model of the change from baseline in naming accuracy adjusted for baseline (with Week 1, 5, or 20 as a categorical variable and a random effect for subject). Similar analyses will be done for the change in accuracy of trained items.

If we accept the null hypothesis, then tDCS is considered clearly ineffective (in improving anomia in stroke patients) and will not be considered for further study. If we reject the null hypothesis, we would consider undertaking a Phase III study of tDCS.

Sample Size Determination

We expect to enroll 50 participants over 4 years, and expect 40-45 will complete the study. We predict no difficulty recruiting at least 10-15 participants with aphasia each year after subacute stroke, as the PI has

Date: March 2, 2021

Principal Investigator: [name], MA

Application Number: IRB00089018

recruited an average of 53 aphasic patients due to acute left hemisphere ischemic stroke each year in her previous studies of aphasia recovery. If sample size in each group is 20, (a total sample size of 40), we will have 89% power to detect a difference in means of 23 (the difference between a A-tDCS mean change in accuracy, μ_1 , of 33 and a sham mean change in accuracy, μ_2 , of 10) assuming that the standard deviation of change for both groups is 22.2 using a two group *t*-test with a two-sided alpha of 0.05. These mean changes for tDCS and sham and standard deviation of change are based on the one published sham-controlled study of tDCS combined with SALT in subacute stroke.

Multiplicity

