Since this is a Phase I/II study, the false positive error rate has been relaxed (Schoenfeld, 1980). For a futility design the type I and type II error rates are reversed as compared to a traditional, superiority hypothesis. For the primary analysis, the probability of incorrectly declaring a drug futile is 0.1 (or 10%, type I error is the false negative rate). Given that the active tDCS comes from a distribution with a mean change of the control group (e.g. the treatment is the same as the sham), the probability of incorrectly moving to a Phase III trial is 0.15 (or 15%, type II error is the false positive rate).

For secondary outcomes and safety analyses, no adjustment of Type I error probability will be considered, since they will be treated as exploratory.

Missing Data

Under the ITT principle, all patients who are randomized are included in the analysis. Therefore, missing data, especially in the primary outcome measure, can be problematic. For the primary futility analysis we will impute missing data using multiple imputation (Rubin, 1987) assuming a monotone missing mechanism and missing is at random (MAR). Similar methods will be employed for secondary analyses and secondary outcomes. For safety data (e.g. AEs) no data imputation will be done.

Interim Analysis

No formal interim analyses are planned.

Adjusting for Covariates

The primary analysis will be adjusted for aphasia type, and baseline aphasia severity (AQ), education, time from stroke onset to time of treatment initiation, and number of previous SLP treatment sessions (prior to our study).

Secondary Analyses

In addition to the primary outcome, several secondary analyses will be conducted. We will examine changes in types of naming errors (defined by the PNT) by tDCS treatment group. The Cinderella story will be analyzed by comparing lexical diversity (VOCD) for nouns, verbs and adjectives; number and types of errors; length and patterns of pauses by treatment group. Pre and post comparisons with both non-aphasic and aphasic speakers from the Aphasia Bank database who share a number of demographic features (e.g., type and severity of aphasia, age, etc.) will also be made. We will also evaluate differences between treatment groups in QOL as measured by the Stroke Impact Scale, mRS, Content Units (CU) and syllables/CU in describing the Cookie Theft picture on the NIH Stroke Scale.

At the end of the study, for the interval scale variables, mean change from baseline to immediate

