4. STUDY DESIGN AND OBJECTIVES

Subjects will be randomized 1:1 to A-tDCS or S-tDCS, with the goal of having 50 randomized subjects for whom the PNT was collected at 1 week post-treatment. This study design will allow us to assess whether A-tDCS over targeted region coupled with computer-delivered SALT is associated with greater gains in accuracy in naming pictures, compared to sham combined with the same computer-delivered SALT in post stroke aphasia.

The primary objective of the study is to determine whether A-tDCS coupled with SALT will improve naming performance of participants with post stroke aphasia more effectively than SALT alone (i.e., the sham condition).

Planned enrollment duration: approximately 4 years (1.04 patients /month)

Duration of treatment phase: 3 weeks

Duration of follow-up in post-treatment Phase: 20 week post treatment (i.e. 23 weeks from baseline)

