8. PRIMARY ANALYSIS

8.1 Primary Outcome

The primary outcome will be the change in the number of correctly named items on the PNT (absolute change from pre-treatment and immediate post-testing). The PNT is administered twice (and averaged to reduce variability) on two consecutive days immediately before treatment starts and twice after treatment is completed. The change will be computed as the difference in the number of correctly named items between the average of the two pre-treatment assessments to the average of the two post-treatment sessions.

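### The protocol treats a non-significant primary test as proof that tDCS does not work, which a trial of this size cannot show; the source and unit of the power inputs also need stating.

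*SAP*

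**What the plan says.** **Decision rule.** Protocol section 2 (Primary Analyses) and section 7c (Statistical Analysis) set the null as equal mean change in the two arms. They then state: "If we accept the null hypothesis, then tDCS is considered clearly ineffective", adding that it would not be taken further. Rejection of the null would lead to consideration of a Phase III trial. SAP 8.2 restates the hypothesis and the null without this consequence. SAP section 2 says that the final SAP overrides the protocol.

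**Error rates.** SAP 8.4 tests the primary analysis at two-sided 0.05. Protocol section 7c (Multiplicity) describes a futility design with reversed errors, in which "the probability of incorrectly declaring a drug futile is 0.1" and the chance of wrongly moving to Phase III is 0.15.

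**Power.** SAP 8.3, and the protocol in sections 2 and 7c, give 89% power with 20 per arm for 33 versus 10, SD 22.2, two-sided 0.05. On the source: "These mean changes for tDCS and sham and standard deviation of change are based on the one published sham-controlled study". The protocol expects 40 to 45 completers. SAP section 4 plans randomization "with the goal of having 50 randomized subjects for whom the PNT was collected at 1 week post-treatment".

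**Outcome.** SAP 8.1: "The primary outcome will be the change in the number of correctly named items on the PNT".

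**The concern.** Failing to reject equality is not evidence of equality. It supports a claim of ineffectiveness only if the confidence interval also rules out every difference worth having, and no text requires that. A 95% CI for active versus sham is planned in SAP 8.5, but for the sensitivity model, and no conclusion is tied to it. At stake is a go/no-go decision: a real, moderate benefit could be recorded as none and the treatment dropped.

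The inputs to the power figure add to this. Protocol section 3 describes the cited study as "comparing three groups of seven patients each who received" cathodal, anodal or sham stimulation. It reports only gains in auditory comprehension: 17% cathodal, 10% sham, 10% anodal. It gives no 33, no SD and no naming result. The protocol's opening summary, discussing acute and subacute stroke, says that "no studies (of which we are aware) have combined A-tDCS with therapy to facilitate" naming. SAP 8.3 states no unit for 33, 10 and 22.2. A reader therefore cannot tell from these documents why 23 is a realistic difference in PNT items.

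**Working it through.** **Inputs.** Difference 33 − 10 = 23, SD 22.2, two-sided alpha 0.05 and 20 per arm (SAP 8.3); 25 per arm is half of the 50 in SAP section 4. All results below are for an unadjusted two-sample t-test and take the SD of 22.2 as true.

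**1. The plan's own figure.** SE = 22.2 × √(2/20) = 7.02; noncentrality = 23 / 7.02 = 3.28; 38 df; critical t = 2.024. The noncentral t gives a power of 0.891, which matches the stated 89%. With 25 per arm it is 0.948.

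**2. What a non-significant result leaves open.** Half-width of the 95% CI = t(0.975, 2n − 2) × 22.2 × √(2/n):
- 20 per arm: 2.024 × 7.02 = 14.2
- 25 per arm: 2.011 × 6.28 = 12.6

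An estimate is non-significant if it is smaller than the half-width, and its CI still contains 23 if it is larger than 23 minus the half-width:
- 20 per arm: 23 − 14.2 = 8.8, so estimates from 8.8 to 14.2
- 25 per arm: 23 − 12.6 = 10.4, so estimates from 10.4 to 12.6

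In those ranges the protocol would declare tDCS ineffective on data compatible with its own design difference.

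**3. Chance of the declaration, by true difference** (1 − power, noncentral t). The value 11.5 is half of 23; 10, 15 and 20 are also illustrative.

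| True difference | 20 per arm | 25 per arm |
|---|---|---|
| 10 | 72% | 65% |
| 11.5 | 64% | 57% |
| 15 | 45% | 35% |
| 20 | 21% | 12% |
| 23 | 11% | 5% |

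The chance exceeds one half only for true differences below about 14.1 (20 per arm) or 12.6 (25 per arm).

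**4. Detectable difference.** At SD 22.2, 80% power requires a true difference of 20.2 with 20 per arm, or 18.0 with 25.

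**5. Source of the inputs.** The power statement needs an anodal mean, a sham mean and an SD of change in naming. From the cited study the documents give an anodal minus sham difference of 10% − 10% = 0 in comprehension, with seven patients per arm. The number 10 recurs for sham, but as a comprehension percentage.

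**The case against.** **The SAP takes precedence.** It restates the hypothesis without the ineffectiveness rule, and its only interpretive guidance in 8.2 is caution if the completer and modified ITT analyses disagree. This confines the defect to the protocol. But silence does not withdraw the rule, and the protocol states it twice.

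**The rule belongs to a futility design.** The Multiplicity text in section 7c reads that way. Its 0.10 and 0.15, however, belong to a reversed design, whereas the stated null is equality, tested at two-sided 0.05. A reader might infer that the trial breaches a promised 10% false-futility rate. That does not follow, because the rate was not set for this test; the two descriptions need reconciling.

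**Most real effects would still be found.** This is partly right. A reader might infer that any effect smaller than 23 would usually be dismissed. The table shows otherwise: at 15 or 20 the declaration is the less likely result.

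**Covariate adjustment in the SAP will raise power.** It may. With an assumed R-squared of 0.25, the residual SD is 22.2 × √0.75 = 19.2 and power at 11.5 rises to 45% / 54% (lost degrees of freedom ignored). The documents give no correlation from which to judge this, and adjustment does not mend the logic of the rule.

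**The cited paper may contain the numbers.** It may. Section 3 of the protocol is a short background summary and does not claim to list every outcome. SAP 8.2 ties the two means to PNT correct, so items can be inferred as the unit. What stands is that the measure, arms and scale are not named.

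**Conclusion.** The decision rule is wrong as written in the protocol and should be corrected. If the SD is 22.2, a non-significant result can coexist with a CI that includes 23, and a true difference of 10 to 15 would be declared ineffective in 45% to 72% of trials with 20 per arm, or 35% to 65% with 25. These figures are for the unadjusted t-test.

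The sourcing point is secondary. A reader might infer that the power calculation is wrong or that the attribution is false. The documents support neither: the arithmetic is correct, and the cited paper is not available here. The supported conclusion is that nothing reported in these documents backs 33, 10 and 22.2 for naming, so they need a source or a label as assumptions.

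**What to change.** 1. In protocol sections 2 and 7c, delete the sentence on ineffectiveness. State there and in SAP 8.2:

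> A non-significant result will be reported with the 95% CI for the adjusted difference from the primary model and will not by itself be taken to show that tDCS is ineffective; the conclusion will be limited to the differences in PNT items that the CI excludes.

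2. If a no-go rule is wanted, tie it to a smallest worthwhile difference in PNT items fixed before unblinding. The value 23 should not serve by default: its basis is the open question, and excluding it says little about smaller benefits. Even if the CI also had to exclude 23, a true 11.5 would be called ineffective in 35% / 42% of trials.
3. Reconcile the futility error rates in protocol section 7c (Multiplicity) with the two-sided 0.05 test.
4. In SAP 8.3 and both protocol power statements, name the measure, arms and unit behind 33, 10 and 22.2, or label them as assumptions in PNT items. Add the 80% detectable differences at SD 22.2 (20.2 with 20 per arm, 18.0 with 25), and note that the protocol expects 40 to 45 completers while SAP section 4 aims for 50.

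Cost: wording only. Enrolment, test and alpha do not change. The power statement will look less favourable, and a null result will support a weaker conclusion.

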8.4 Multiplicity

The primary analysis and sensitivity analyses will be tested at two-sided alpha of 0.05. For secondary outcomes, no adjustment of Type I error probability will be considered, since they will be considered supportive of the primary analysis. Tests for interaction with baseline covariates and treatment will use two-sided alpha of 0.10, since they will be treated as exploratory.

8.5 Missing Data

For the primary analysis, for participants who do not complete the 1 week post-treatment assessments, the post-treatment value will be imputed using a multiple imputation approach assuming a FCS missing mechanism and missing is at random (MAR).

As a sensitivity analysis with the modified ITT sample, the primary outcome analysis will be repeated using all available follow-up data (without explicit imputation) in a mixed effects model of the change from baseline in naming accuracy adjusted for baseline (with week (1, 5, or 20 weeks post-treatment) as class variable and a REPEATED statement). The model will include the baseline covariates used for the primary analysis as fixed effects.

The statistical model will be a repeated measures model (SAS® MIXED procedure with REPEATED subcommand) assuming a compound symmetry (CS) covariance structure.

```
PROC MIXED;
  CLASS SUBJID ARM VISITNUM TYPE;
  MODEL CHANGE= ARM|VISITNUM WABAQ TYPE AGE;
    REPEATED VISITNUM / TYPE= CS SUBJECT=SUBJID R RCORR;
  LSMEANS ARM*VISITNUM/pdiff CL;
RUN;
```

The least square (adjusted) mean for each treatment group, and the 95% confidence interval for the comparison (active vs. sham) will be presented at 1, 5, 20 weeks post treatment.

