Date: March 2, 2021

Principal Investigator: [name], MA

Application Number: IRB00089018

post-testing in secondary outcome measures will be reported by treatment group along with the 95% confidence intervals. Treatment comparisons will be made with a paired t- test. For binary variables, the proportion of subjects immediately post-testing will be reported by treatment group along with the 95% confidence intervals.

Post-Testing Phase

The longer follow-up post-testing phase will provide exploratory information on whether the immediate post-testing improvement after three weeks of treatment can be sustained. The mean (95% CI) changes from baseline to immediate (within one week) post-testing, five weeks (after the end of treatment) post-testing and 20 weeks (after the end of treatment) post-testing will be reported. Box and whisker plots will be produced to show the distribution of naming accuracy over time by treatment group. To explore the longitudinal data, a general linear mixed model (GLMM) will be constructed by tDCS group for the dependent variable (anomia). The GLMM will incorporate random subject effects to account for repeated measurements being made on subjects; the model will include time, aphasia type, severity, and clinical center as independent variables. A similar modeling approach may be applied to other secondary outcomes.

Safety Analyses

All adverse experiences will be summarized in terms of frequency, severity and relatedness to the study treatment using the MedDRA code. All subjects who received tDCS will be included in the safety analysis. At the end of the study, the cumulative incidences of adverse events are compared between the two treatment groups using Fisher's exact test at the two-sided alpha level of 0.05.

The repeated measures of the FACES pain rating scale will be compared by treatment group by fitting a repeated measures proportional odds model.

DSMB Reporting

The study biostatistician will generate closed and open DSMB reports semi-annually or more frequently, as determined by the DSMB. Each DSMB report provides cumulative summary statistics on enrollment; subject status in the study (e.g., number completed study, drop outs, etc.); baseline characteristics; safety data, including AEs and SAEs; and data quality information. The statistics for the closed DSMB Reports are provided by treatment group displayed as A or B. The open report contains aggregated statistics only, i.e., not by treatment group.

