8.2 Statistical Hypotheses

The Primary Hypothesis 1a: A-tDCS over a targeted region coupled with computer-delivered SALT is associated with greater gains in accuracy in naming pictures, compared to sham coupled with the same computer-delivered SALT in post stroke aphasia. To test this hypothesis, we will compare the change in means of outcome measures in the group who received sham versus the group who received tDCS. The primary outcome variable will be change in accuracy of naming untrained items within one week after treatment ends. The null hypothesis is $H_0: \mu_1 = \mu_2$, where μ_1 is the mean change in accuracy of naming untrained items (PNT correct) between baseline and 1 week post-treatment in the A-tDCS group and μ_2 is the mean change in the sham group. The primary analysis will compare change between groups (A-tDCS versus S-tDCS) using multiple regression and will be adjusted for aphasia type (Anomia, Broca, or other type), baseline aphasia severity (AQ), and age. The primary analysis will be performed using both the Completers and Modified Intent-to-treat Samples. If these two analyses are not consistent, then the trial findings will be interpreted with caution.

Sensitivity analyses will be done for the change in accuracy of trained items using the same approach. Naming errors will also be analyzed and categorized as semantic related, semantic unrelated, real words related phonologically, non-words related phonologically, mixed semantic/phonological, abstruse neologisms, and no response. Additional sensitivity analyses will adjust for education and time from stroke onset to time of treatment initiation in addition to the covariates included in the primary model.

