9. HYPOTHESIS 1B

Hypothesis 1b: To address the hypothesis that the effect of A-tDCS will be greater in subacute stroke than reported in chronic stroke, the mean (95% CI) changes from baseline to 1 week, 5 weeks, and 20 weeks in PNT+Naming 80 after the end of treatment will be reported for the subacute patients enrolled in this project and the chronic patients from the CATES trial ([name], PI).

A figure of the adjusted mean of adjusted means (95% CI) at each time point for SLISSE Active, Sham using the repeated measures model described above will be shown alongside the adjusted means from CATES Active, Sham.

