10. SECONDARY ANALYSES

Secondary analyses will evaluate the effect of A-tDCS vs sham on change in lexical features of discourse, Content Units (CU) and syllables/CU in describing the Cookie Theft picture, HANA, NIH Stroke Scale, SIS, mRS, and PHQ-9.

For continuous measures, the secondary analyses will be adjusted for aphasia type (Anomia, Broca, or other type), baseline aphasia severity (AQ), and age using a linear mixed effects regression to compare treatment groups. The model will include repeated measures of change from baseline to 1, 5, 20 weeks post and visit will be a classification variable with interaction terms for visit*treatment group (SAS PROC MIXED with a REPEATED subcommand).

```
PROC MIXED;
  CLASS SUBJID ARM VISITNUM TYPE;
  MODEL CHANGE= ARM|VISITNUM WABAQ TYPE AGE;
    REPEATED VISITNUM / TYPE= CS SUBJECT=SUBJID R RCORR;
  LSMEANS ARM*VISITNUM/pdiff CL;
RUN;
```

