Hypothesis 2b: To address the hypothesis that SSRI use since stroke onset is associated with greater gains with all treatments in the subacute period, independently of depression, we will collapse participants across treatment groups, and compare the primary outcome measures for participants who have continuously taken SSRIs to participants who have not taken SSRIs. If SSRI use enhances plasticity at the subacute stage, it might augment the effect of A-tDCS and naming therapy without tDCS. Participants who have taken SSRIs for only part of the time will not be included in the analysis. The adjusted mean change (95% CI) in naming accuracy on untrained stimuli from baseline to 1 week, 5 weeks, and 20 weeks post-treatment for the SSRI-treated and the SSRI-untreated groups will be estimated using a mixed effects model adjusting for treatment group, baseline naming accuracy, time (with week 1, 5, or 20 as a categorical variable and a random effect for subject), and any baseline subject characteristic found to be statistically significant in the primary or subgroup analyses. We will then evaluate the independent effects of SSRI use, depression (measured at each time point with PHQ-9 score of ≥ 15), and tDCS vs sham on the primary outcome graphically. Although we may not have the power to detect a significant effect of SSRIs, a few studies with similar small numbers have reported significant effects of SSRIs on stroke recovery measured with less sensitive measures such as the mRS. The goal of this exploratory aim is to determine whether or not we need to control for SSRI use in a subsequent clinical trial of A-tDCS in subacute stroke.

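### The supportive repeated-measures models impose one common variance on change at 1, 5 and 20 weeks, so their week-specific 95% CIs are miscalibrated if the variance differs between visits

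*SAP*

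**What the plan says.** SAP 8.5 repeats the primary outcome analysis in a repeated-measures model of change from baseline, "assuming a compound symmetry (CS) covariance structure". The active-versus-sham comparison and its 95% CI "will be presented at 1, 5, 20 weeks post treatment".

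The same structure reaches three other analyses:

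- SAP 10 uses identical code for the continuous secondary outcomes: "REPEATED VISITNUM / TYPE= CS SUBJECT=SUBJID R RCORR".
- SAP 9 draws the Hypothesis 1b figure, with a 95% CI at each time point, "using the repeated measures model described above".
- SAP 11, Hypothesis 2b, has no code, but adjusts for "time (with week 1, 5, or 20 as a categorical variable and a random effect for subject". If that effect is a random intercept, the marginal covariance is again compound symmetry.

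The protocol's Post-Testing Phase paragraph (section 7c) is similar: "The GLMM will incorporate random subject effects to account for repeated measurements being made on subjects". The SAP states that its final version overrides the protocol.

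No heterogeneous-variance structure, robust standard error or check of the assumption is planned. The R and RCORR options only print the fitted matrix.

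Two analyses lie outside this point. The primary analysis (SAP 8.2) compares the 1-week change "using multiple regression and will be adjusted for aphasia type (Anomia, Broca, or other type), baseline aphasia severity (AQ), and age", and the PROC MIXED block in SAP 11 has no REPEATED statement.

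**The concern.** Compound symmetry allows one variance and one correlation for all three visits. That does little harm when a model reports only an overall treatment effect. Here each model reports intervals week by week, and each week's standard error is built from a variance pooled over all weeks.

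Equal variance at the three visits is not a safe default in this population. Patients enter within three months of stroke, and the protocol's background says that recovery falls mostly in the first few months and that gains in therapy are variable. Change measured 20 weeks after treatment spans far more of that recovery than change measured at 1 week.

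Two things are at stake. One is the calibration of every week-specific interval from these models. The other is how clearly the 8.5 model works as a check on missing-data handling. The primary regression uses only the 1-week residual variance, whereas the sensitivity model pools three visits. The two week-1 intervals could therefore differ in width for a reason unrelated to missing data.

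**Working it through.** **Inputs from the documents.** 20 per group, difference 23, two-sided alpha 0.05, and one SD: "assuming that the standard deviation of change for both groups is 22.2" (SAP 8.3). No SD is given separately for week 5 or week 20, and no between-visit correlation is given. The visit SDs, correlations and dropout pattern below are assumptions.

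**Step 1: the plan's own figure.** The noncentrality is 23 / (22.2 × √(2/20)) = 23 / 7.02 = 3.28. With 38 degrees of freedom, exact two-sided t-test power is 0.891, so the stated 89% reproduces. It belongs to the 1-week comparison and does not involve the repeated-measures covariance.

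**Step 2: what compound symmetry does.** With complete balanced data, each week's contrast gets the same standard error, SD_avg × √(2/n), where SD_avg is the square root of the mean of the three variances. Coverage at week t is then 2Φ(1.96 × SD_avg / SD_t) − 1.

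- SDs 20/22/25: SD_avg = √((400 + 484 + 625)/3) = √503.0 = 22.43.
- SDs 18/22/28: SD_avg = √((324 + 484 + 784)/3) = √530.7 = 23.04. The week-1 standard error is 23.04/18 = 1.28 times the correct one (28% too large). The week-20 standard error is 23.04/28 = 0.82 times it (18% too small).

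| Assumed SDs, weeks 1/5/20 | Coverage of nominal 95% CI, weeks 1/5/20 |
|---|---|
| equal | 95.0 / 95.0 / 95.0% |
| 20/22/25 | 97.2 / 95.4 / 92.1% |
| 18/22/28 | 98.8 / 96.0 / 89.3% |
| 25/22/20 | 92.1 / 95.4 / 97.2% |

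**Step 3: interval widths on the plan's scale.** Take 22.2 as the week-1 SD and assume ratios 1 : 1.25 : 1.5, that is 22.2, 27.8 and 33.3. SD_avg is 28.12, so compound symmetry gives a full width of 2 × 1.96 × 28.12 × √(2/20) = 34.9 items at every week. The correct widths are 27.5, 34.4 and 41.3. Coverage is 98.7/95.3/90.2%.

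**Step 4: simulation.** REML fits, 20 per arm, arm-by-visit model with two covariates, correlations 0.8 (weeks 1–5), 0.7 (weeks 5–20) and 0.6 (weeks 1–20), 500 runs per scenario, Monte Carlo error about ±2 points. Simple rather than Kenward-Roger degrees of freedom were used. Dropout, where present, was about 20% by week 20.

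| SD ratio, dropout | Compound symmetry | Unstructured |
|---|---|---|
| 1:1:1, with dropout | 95.4 / 93.4 / 95.2% | 95.4 / 93.2 / 95.2% |
| 1:1.25:1.5, none | 98.0 / 96.2 / 92.4% | 95.2 / 95.2 / 95.8% |
| 1:1.25:1.5, with dropout | 97.8 / 94.0 / 90.4% | 95.0 / 94.8 / 95.6% |
| 1:1.5:2, with dropout | 99.0 / 93.2 / 83.2% | 94.8 / 93.0 / 93.2% |

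The first row has unequal correlations but equal variances, and compound symmetry does as well as the unstructured model there. Unequal variance is therefore the driver. The unstructured model was estimable at this sample size.

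**The case against.** The strongest reply has three parts.

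**Nothing decisive depends on these models.** The primary test is a separate 1-week regression, and the protocol ties the Phase III decision to its null hypothesis. The protocol calls the longer follow-up exploratory. The SAP's primary objective does not mention duration of benefit, although the protocol's does. SAP 8.4 treats secondary outcomes as supportive. All of this stands, and it limits the importance of the point.

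**The direction of error is unknown.** A reader might infer that week-20 intervals will be too narrow and so inflate false claims of lasting benefit. The documents do not support that. They give one SD, and the PNT score is a count with a maximum, so continuing recovery could compress the spread as easily as widen it. With shrinking variance, week 20 becomes conservative and week 1 too narrow. This stands as to direction, but it does not rescue the assumption, since a change either way breaks it.

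**The calculation does not transfer directly to every secondary outcome.** No SDs are given for those outcomes. The protocol's diagnostic-testing list schedules the NIHSS and Cookie Theft repeats at weeks 5 and 20 only, while SAP 10 lists all three weeks. With two visits pooled, the effect is milder: SDs 22/25 give SD_avg = √554.5 = 23.55 and coverage of 96.4/93.5%. This also stands.

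A further tempting argument is that the unequal visit spacing is itself the harm. The coverage formula contains no correlation term, and the simulation found little effect from unequal correlations alone.

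**Conclusion.** The point holds conditionally. The SAP 8.5 sensitivity analysis, the Hypothesis 1b figure and the continuous secondary outcomes all assume equal variance across visits while reporting intervals visit by visit. Hypothesis 2b does the same if its subject effect is a random intercept. Where variance differs, no week is guaranteed a correct interval, and the plan has no safeguard.

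Under the assumed SDs, the worst-week coverage is about 92% for moderate change in either direction (20/22/25 or 25/22/20). It is about 89% for 18/22/28, an error rate of roughly 11% instead of 5% at that week. With equal variances there is no loss.

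A reader might also infer that the trial's main result is at risk. It is not: the 1-week multiple regression and its 89% power do not use this covariance structure. The change is worth considering because it is cheap, not because a confirmatory conclusion depends on it.

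**What to change.** SAP section 2 already foresees an update before database lock and unblinding, so the change can be prespecified there:

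- In 8.5, replace the compound symmetry sentence with an unstructured covariance.
- In both PROC MIXED blocks (8.5 and 10), use TYPE=UN in place of TYPE=CS and add DDFM=KR to the MODEL statement. SAP 9 then inherits the change.
- In SAP 11, give the Hypothesis 2b model the same structure in place of the random subject effect.
- Name heterogeneous compound symmetry (TYPE=CSH) as the fallback if the unstructured model does not converge. It frees the three variances, which are what matter, with 3 + 1 = 4 parameters. Heterogeneous Toeplitz is a poorer choice: at 3 + 2 = 5 parameters it saves only one, and its lag structure equates the week 1–5 and week 5–20 correlations although the gaps are 4 and 15 weeks.

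The cost is 6 covariance parameters instead of 2, and slightly less precise intervals if the variances are in fact equal. In the equal-variance simulation with dropout, mean widths were 28.4, 29.1 and 30.5 items with the unstructured model, against 28.2, 29.0 and 29.8 with compound symmetry. No extra data or participants are needed.
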